We previously tested the hypothesis that adaptation to upward-shifting prisms, producing a downward recalibration in pointing, would reduce forward stepping time in patients with Parkinson's disease. The rationale for this approach was that, based on the results of Tilikete and colleagues, adaptation to upward-shifting prisms would shift the standing posture forwards. In a study of 16 patients we found that a single five-minute session of prism adaptation reduced forward stepping time by an average of 183ms (~10% reduction) [4]. Backward stepping time was unchanged, and a test of adaptation to downward-shifting prisms with control participants showed no effect on forward or backward stepping. This study provides proof-of-concept that prism adaptation can reduce forward stepping time in patients with Parkinson's disease using a laboratory-based measure of stepping.

2. Objectives and Hypotheses

Objective: To compare the effect of two weeks of twice-daily adaptation to upward prismatic shifts in the visual field vs. two weeks of sham adaptation on measures of posture and gait in patients with idiopathic Parkinson's Disease.

Hypotheses: Compared to patients who undergo sham prism adaptation, patients who complete two weeks of real prism adaptation therapy will show reduced stepping initiation times, greater displacement of the body over the feet during stepping initiation, and increased self-report of confidence while walking. We will also measure a number of other common clinical indicators to determine whether prism adaptation improves motor performance and postural responses to external perturbations.

3. Study Design

Describe all study procedures, materials, and methods of data collection:

The study will have a longitudinal, repeated-measures, between-subjects, double-blind, sham-controlled design. Thirty patients with idiopathic Parkinson's Disease will be randomly assigned to undergo two weeks of twice-daily sessions of adaptation to upward-shifting prisms, or sham adaptation (in which patients perform the same sensory-motor task while wearing goggles fitted with neutral lenses). Measures of posture and gait (see below) will be recorded in two sessions: pre- and post-treatment. Additional long-term follow-up will be obtained through questionnaires by mail at one week, one month and three months post-treatment. The timeline for the research sessions, intervention period and follow-up questionnaires are outlined in Figure 1.

Procedures:

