Functional Gait Assessment. This is a reliable and valid assessment of assessing ten gait-related measures (e.g. stepping over a box, climbing stairs). A total score out of 30 is calculated, with lower scores indicating greater impairment.

2) Mechanized measures

We will use two sophisticated measurement systems to measure musculoskeletal factors related to posture and gait.

Assessment of postural stability using the SMART EquiTTest Balance Master. This system uses a force plate to measure center of gravity and postural control. Patients stand on a force plate while wearing a support vest. We will use two protocols provided by this system. The Motor Control test assesses the ability of the patient to recover their standing balance after an unexpected translation of the force plate. The Limits of Stability test measures the maximum distance a person can intentionally displace their center of gravity in a given direction without losing balance, stepping or reaching for their center of gravity in a given direction without losing balance, stepping or reaching for assistance. For both of these tests a comprehensive performance report is provided, including measures of reaction time and amplitude of movements.

We will also perform a third test that is not part of the standard EquiTTest protocol. For this, we will ask participants to take a step forward. We will measure the displacement of the center of gravity over the center of pressure (i.e., the movement of the body over the feet) using the same performance report as is used for the Limits of Stability test. This non-standard test will allow us to directly test our hypothesized mechanism of prism adaptation treatment: namely that it increases the displacement of the body over the feed when patients initiate walking.

Assessment of gait using the ActiveStep. This system is a mobility stimulator that enables safe measurement of walking and propensity to fall with and without environmental perturbations. A number of parameters are measured, including trunk extension and flexion velocity and step length and speed.

3) Self-report questionnaires

Four questionnaires will be used to measure patients' perceptions of their risk of falling and their confidence in safely performing daily activities. These will be administered five times: in the pre-test, post-test, one-week follow-up, one-month follow-up, and three-month follow-up.

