Falls Efficiency Scale. This ten-item self-report questionnaire asks people to rate their confidence in performing daily activities without falling. Responses are given on a scale from 0 ("very confident") to 10 ("not very confident") and a total score out of 100 is computed.

Activities-specific Balance Confidence Scale. This 16-item self-report questionnaire is similar to the Falls Efficiency Scale, but has greater sensitivity to gait impairments in more ambulatory patients.

PDQ-39 (mobility and activities of daily living sections). This self-report questionnaire is the most widely-used Parkinson's Disease specific measure of health and daily function. Participants indicate the extent to which they have experienced problems with different aspects of mobility and self-care. Each item is scored from 0 ("never have problems") to 4 ("always have problems"), and a percentage is calculated.

New Freezing of Gait Questionnaire. This nine-item questionnaire detects and evaluates the impact and severity of freezing of gait on locomotion and daily activities.

The following questionnaire will be administered in the pre-test only:

Patient-Centered Outcome Questionnaire – Parkinson's Disease. This four-item questionnaire measures patient's expectations of treatment outcome. The data from this questionnaire will be used in post-hoc analysis to regress out any potential effects of patient expectation (e.g. placebo effect) on perceived improvements.

The following questionnaire will be administered in the post-tests only:

Post-intervention questionnaire. This questionnaire asks questions specific to the participant's experience of the prism adaptation treatment. There are two versions of this questionnaire. Version 1 is to be administered in visit 2. In Version 1 the participant is asked to rate the extent to which they felt any adverse effects, the

degree to which they enjoyed the treatment, and the extent to which they feel their symptoms have changed as a result of treatment. Version 2 is to be included in the post/telephone follow-up questionnaires and contains only the questions about the extent to which the participant feels their symptoms have changed as a result of treatment.

4. Analysis

Describe any qualitative tests and measures as well as quantitative methods:

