b. Confirm that risks to subjects have been minimized, by use of procedures which are consistent with sound research design and which do not unnecessarily expose subjects to risk:

Visual adaptation has a minimal risk: it is performed while seated, thus has the potential to provide a safe, indirect means to treat gait impairment.

c. Describe why all the risks to subjects are reasonable in relation to both anticipated benefits and the knowledge expected to be gained from the study:

The research is expected to lead to new insights into the treatment of gait problems in patients with Parkinson's Disease. Furthermore, it is possible that those patients who are randomly assigned to receive prism adaptation treatment will benefit individually by experiencing an improvement in gait initiation. All patients may also gain an increased understanding of their symptoms through the pre- and post-assessment sessions. Considering these potential benefits, the minor and unlikely risks involved in participation are reasonable.

7. Unexpected Events or Incidental Findings

Note: It may be important to consider the potential for certain unanticipated events to occur, for example:

- finding an anomaly in a MRI
- discovering child abuse
- causing distress in interviews of a sensitive nature

Describe potential events and provide a plan of action:

One item in the UPDRS includes depression with suicidality. If the patient is suicidal, we will escort subject to the ED for evaluation for depression.

8. Placebo Use or Inconsistency with Standard of Care

Does any part of this study involve the use of a placebo or procedures that are inconsistent with the standard of care at Dartmouth-Hitchcock Medical Center?

No Yes

If Yes, explain how the use of placebo or non-standard of care therapy may affect risks for participants, addressing the following:

- The safety and efficacy of other available therapies
- The maximum total length of time a participant may receive placebo on study
- The greatest potential harm that may result from not receiving or delaying effective therapy
- Safeguards for the participants receiving placebo or non-standard of care therapy

9. Genetics

Does any part of the study involve genetic analysis of biological specimens?

No

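### Adverse effects are asked about at one of four post-baseline contacts and no described instrument counts falls, so later harms and daily-life falls would not be recorded as events by arm

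*Combined protocol and SAP*

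**What the plan says.** **Adverse effects.** Section 3 (Study Design, Self-report questionnaires) describes two versions of the post-intervention questionnaire. "In Version 1 the participant is asked to rate the extent to which they felt any adverse effects", and "Version 1 is to be administered in visit 2". Version 2 goes out with the follow-up forms and "contains only the questions about the extent to which the participant feels their symptoms have changed as a result of treatment". The opening of Section 3 sets the follow-up times: "Additional long-term follow-up will be obtained through questionnaires by mail at one week, one month and three months post-treatment".

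**Falls.** The four repeated questionnaires are introduced as measuring patients' "perceptions of their risk of falling and their confidence in safely performing daily activities". The Falls Efficiency Scale "asks people to rate their confidence in performing daily activities without falling". The mechanized measures include a Motor Control test, a Limits of Stability test and an ActiveStep assessment that covers propensity to fall. These are done at the pre-test and post-test only.

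**Intended effect and risk.** Section 1 (Previous research) gives the rationale that "adaptation to upward-shifting prisms would shift the standing posture forwards". Section 6b argues for minimal risk because "it is performed while seated, thus has the potential to provide a safe, indirect means to treat gait impairment". Section 6a names fatigue and discomfort as the risks.

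**Analysis and monitoring.** Section 4 has no adverse-event or falls analysis. Section 5 says only that use of a DSMB will be looked into.

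**The concern.** The Section 6b argument covers the pointing task. The effect under test appears after the goggles come off, when the patient stands and starts to walk with the body further forward over the feet. Section 10c admits patients up to Hoehn and Yahr stage IV, with an abnormal gait, freezing or postural stability item and a Timed Up and Go above 12 seconds. Sessions are self-guided at home. In this setting falls are a natural safety outcome to record, whichever way the treatment moves them.

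Two of the hypothesised benefits are greater displacement of the body and greater confidence in walking. Neither result, taken alone, shows whether patients fell more or less often. If the plan is followed exactly, the final report could not state how many patients in each arm fell, when, or with what injury, nor which adverse effects arose after visit 2. Section 1 asks whether the technique is clinically viable, and a reader of the results would want those facts.

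**Working it through.** **1. Count the contacts.** The post-baseline contacts are visit 2 (taken as the post-test, the second of the two assessment sessions), one week, one month and three months.

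| Contact | Adverse-effect question | Fall count described | Laboratory balance tests | Repeated questionnaires |
|---|---|---|---|---|
| Visit 2 | Yes (Version 1) | No | Yes | Yes |
| One week | No (Version 2) | No | No | Yes |
| One month | No (Version 2) | No | No | Yes |
| Three months | No (Version 2) | No | No | Yes |

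Adverse effects are asked about at 1 of 4 contacts and falls are counted at 0 of 4. The planned self-report ANOVA in Section 4 also leaves out the one-week contact, the follow-up nearest to treatment.

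**2. Time covered.** Treatment lasts 14 days. Taking three months as 91 days, the window is 14 + 91 = 105 days. The Version 1 question can cover 14/105 = 13%, and 91/105 = 87% comes after it. This is calendar time, not exposure: all treatment falls inside the covered 14 days.

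**3. Size of any safety comparison.** Section 10b aims for 32 completers with up to 20% withdrawal: 32/(1 − 0.20) = 40, which matches the plan's 40 approached. That gives 16 per group.

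**4. What a fall count could show.** The documents give no fall rate, so all risks here are assumptions.

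- *Upper bound with zero fallers*, one-sided 95%: 1 − 0.05^(1/n). For n = 16 this is 17.1%. For n = 15, half of the 30 patients stated in Sections 3 and 10a, it is 18.1%.
- *Chance of seeing at least one faller in 16*: 1 − (1 − p)^16. This is 56% at p = 5%, 81.5% at 10% and 97% at 20%.
- *Chance of zero fallers in 16*: (1 − p)^16. This is 18.5% at p = 10%, 2.8% at 20% and 0.3% at 30%. The zero-event bound is therefore a best case in a population chosen for gait impairment.
- *Power to show more fallers on prism*, Fisher's exact test, two-sided 0.05, 16 per group, assumed sham risk 10% to 40%:

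| Excess on prism | Power |
|---|---|
| 20 points | 12–17% |
| 30 points | 27–36% |
| 40 points | 50–58% |

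By normal approximation, 80% power for a 20-point excess needs 62 to 97 per group over the same range. Counting falls would give description and intervals, not a usable test.

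**The case against.** A reader might infer that harm would go unseen, or that any safety claim would rest on perception alone. The documents do not support either reading.

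- The Motor Control test measures recovery after an unexpected platform movement, Limits of Stability measures controlled displacement without loss of balance, and ActiveStep addresses propensity to fall. With the Functional Gait Assessment, Timed Up and Go and neurological examination, these are taken in both arms before and after treatment. If patients recovered balance less well after prism training, these tests could show it at visit 2.
- Version 1 asks about adverse effects in general after the whole treatment period, so a patient could have a fall in mind when answering.
- After visit 2, the confidence scales, the PDQ-39 sections on mobility and daily activities, the freezing questionnaire and the symptom-change questions are repeated. Harm could appear there as worsening.

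A further inference would be that the treatment raises fall risk. No passage says so. Section 1 describes too little forward movement as the deficit, so the shift is meant to be corrective, and Section 6a reports no serious adverse effects of prism adaptation. More falls on prism is a hypothesis to be checked. The Section 6a record, however, refers to healthy people and stroke patients. The Parkinson's study cited in Section 1 had 16 patients and one five-minute session, against 2 × 14 = 28 sessions here. The persistence of effect is likewise argued from stroke research.

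It is also fair to say that the questionnaire items are not reproduced, so the claim must be limited to instruments as described, and that a reporting route outside these documents cannot be excluded. Finally, follow-up is secondary to the post-treatment endpoint, and the trial is too small to test falls.

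What remains is that none of these measures is described as recording an event, a date or an injury, that the laboratory tests end at visit 2, and that the adverse-effect question is removed from follow-up by an explicit rule.

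**Conclusion.** The point holds as a gap in recording. Adverse effects are asked about at 1 of 4 post-baseline contacts, no described instrument counts daily-life falls, and about 87% of the observation window follows the only adverse-effect question. Under the plan as written, falls and later adverse effects would not be available as events by arm.

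Indirect signs of harm could still be seen, so this is less direct and less complete capture of harm, not blindness to it. The conclusion rests on the instruments as summarised in Section 3, on three months being about 91 days, and on no other reporting route existing. The power and bound figures rest on 16 per group and on assumed fall risks. They show that the benefit of a change is descriptive reporting with intervals. The change is worth making because it is specific to the intended effect of this treatment and costs little.

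**What to change.** - **Version 2:** keep the Version 1 adverse-effect question at one week, one month and three months.
- **Falls item:** ask for the number and dates of falls since the last contact, at visit 2 (covering the 14-day home period) and at each follow-up. At the pre-test, ask for recent fall history over a stated look-back period.
- **Section 4:** report adverse effects and falls by arm, descriptively and with confidence intervals, beside the confidence and displacement results. State that about 16 per group cannot confirm or exclude a moderate excess of falls.
- **Section 6b:** address the after-effect on standing and walking as well as the seated task.

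The cost is a protocol and questionnaire amendment and one or two extra items on forms already in use. No visit or contact is added. The downside is slightly longer forms and a slightly less favourable risk section.

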All data will be anonymized and analyzed using non-parametric and parametric standard tests using SPSS software. Statistical analyses will be performed with appropriate correction for multiple comparisons.

The endpoints will be the post-treatment clinical assessment session.

Scores for each of the outcome measured will be analyzed using two-by-two, repeated measures ANOVAs, with Group (sham, prism) and session (pre, post) as independent factors. In the case of the self-report measures, two-by-four repeated measures ANOVAs will be performed with Group (sham, prism) and session (pre, post, one-month, three-months) as independent factors. Post hoc analyses will be in the form of t-tests (or non-parametric equivalents), corrected for multiple comparisons. These tests will determine if prism adaptation improves performance to a greater extent than sham treatment. In addition, 95% confidence intervals will be constructed around mean performance for each group before and after sham or prism treatment to test whether the group performance deviates significantly from established normative data or diagnostic cut-offs (e.g., for the UPDRS).

5. Study Progress Monitoring

Note: appropriate monitoring may include periodic assessment of the following:

- data quality
- timelines
- recruitment and enrollment

Provide a description of the methods which will be used to determine the progress of the study, including periodic assessments of data quality, timelines, recruitment, and enrollment as appropriate:

We will check into using the psychiatry DSMB.

6. Risks & Benefits

Note: Risks may be physical, psychological, social, legal, economic, to reputation, or others.

a. Describe any potential risks, their likelihood and seriousness:

There is a minor risk that the treatment or assessment procedures will result in some fatigue or discomfort. This is expected to be short-lived, and would be no greater than that involved in patients' normal physical therapy. To minimize the risk of fatigue during the pre- and post-treatment assessments, patients will be provided with breaks between tasks as required. Prism adaptation has been used for studying sensory-motor integration in healthy individuals for over a century, and in the treatment of stroke patients with hemispatial neglect for over ten years. In this time there have been no reports of serious adverse effects.

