Yes, the study is based on the premise that a link between a genotype or a biomarker and a specific disease or condition is clinically useful in predicting the development of that specific disease or condition. **Please complete the [Genetic Research Form](#) and upload it to the ‘Supporting Documents’ page in Rapport.**

-OR -

Yes, the study is looking for an association between a genotype or a biomarker and a specific disease or condition, but at this point it is not clear if the genetic marker has predictive value. The uncertainty regarding the predictive value of the genetic marker is such that studies in this category will not involve referral of participants to genetic counseling; however, participants will be informed of genetic testing in the consent form. **Please comment:**

10. Equitable Participant Selection

a. Estimated number of participants at Dartmouth CPHS reviewed sites:

Approximately 30 patients will be enrolled in the study at Dartmouth-Hitchcock Medical Center.

b. Provide a justification of the proposed sample size

For the methods specified above, there is no well-established method for calculation of group size as yet. We can, however, draw on experience from previous experiments, indicating what is the minimal/optimal number of participants for detecting significant effects. Previous studies that tested the effects of a similar prism adaptation treatment protocol on sensory and motor problems in stroke patients have used between 12 and 16 patients per group (Frassinetti, Serino). We aim to approach 40 patients with at least 32 completing the study (16 per group), which will provide a sufficient dataset even if up to 20% of participant withdraw before the completion of the study

c. Define the target population:

The patient population that will be targeted are the patient is referred for Parkinson's disease with gait impairment at Dartmouth-Hitchcock Medical Center

Inclusion/Exclusion Criteria:

Inclusion

- Diagnosis of idiopathic Parkinson's Disease
- Referral for gait training
- Aged 40-85
- If the subject is taking CNS-acting CNS-acting medications (benzodiazepines, hypnotics, antidepressants), regimen must be stable for 30 days prior to baseline visit
- Subjects with Stage II.5 – Stage IV (Hoehn and Yahr scale) where stage II.5 is bilateral involvement with axial involvement, but without balance difficulty, to Stage IV where one has severe disability but is still able to walk or stand unassisted.

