- Subjects with any of the following abnormal scores (greater than 0) in the MDS-UPDRS Part III:
a) Part III.10 Gait; b) Part III.11 Freezing of gait c) Part III.12 Postural Stability
- Subjects with a Timed up and go test > 12 seconds

- Right-handed participants are preferred due to the cortical lateralization of functions related to sensorimotor adaptation and postural control. However we will recruit left-handed participants if there are insufficient right-handed volunteers.

Exclusion

- Subjects with a known psychiatric comorbidity that in the investigator's opinion would compromise participation in the study
- Subjects with a neurologic diagnosis, other than Parkinson's disease that can cause imbalance and gait impairment. (e.g., multiple sclerosis, stroke, subdural hematoma, peripheral neuropathy)
- Injury or impairment to the right arm (other than that which is due to Parkinson's Disease) that would affect pointing movements
- Subjects with normal score on UPDRS part III
- Classified as legally blind or lacking sufficient visual acuity to view the target and pointing hand during prism adaptation.
- Lacking sufficient understanding of verbal and written information in English to complete any of the consent screening forms

d. Vulnerable populations

Note: Certain populations are considered vulnerable to coercion and undue influence and are provided with additional protections when participating in a research study.

Identify any of the below populations which you plan to recruit for this study. In addition, complete the form(s) linked with each population as necessary and upload on the 'Supporting Documents' page in Rapport.

- [Pregnant Women, Fetuses and Neonates](#)
- [Children](#)
- [People with impaired decision-making capacity](#)

The following populations may also be considered vulnerable to coercion or other undue influence:

- Prisoners
- People who are economically disadvantaged
- The elderly
- People who are illiterate or do not speak English
- Students and employees

Describe any other potentially vulnerable population(s) and the additional protections provided to them:

Not applicable. We will be recruiting the elderly but will not be excluding people regarding socioeconomic status.

11. Recruitment

Describe method(s) of recruitment. Associated advertisements and other materials to be used for recruitment should be uploaded to the 'Consent Forms and Recruitment Materials' page in Rapport.

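### The two-by-two ANOVA reduces to an unadjusted change-score test; ANCOVA on the pre-test is usually more precise and costs at most about 3.6% of variance at 32 completers

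*Combined protocol and SAP*

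**What the plan says.** Section 4 (Analysis) states that scores will be "analyzed using two-by-two, repeated measures ANOVAs, with Group (sham, prism) and session (pre, post) as independent factors". The self-report questionnaires are treated separately: "two-by-four repeated measures ANOVAs will be performed with Group (sham, prism) and session (pre, post, one-month, three-months) as independent factors". Post hoc t-tests or non-parametric equivalents follow, and then the sentence "These tests will determine if prism adaptation improves performance to a greater extent than sham treatment". That sentence could refer to the ANOVAs or to the post hoc tests, and no term is named as decisive. Section 4 also says "Statistical analyses will be performed with appropriate correction for multiple comparisons", without a method or a count of tests.

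No section adjusts an outcome for its own pre-test value. The only adjustment mentioned, in section 3 under the questionnaires, is a post hoc regression on the patient's expectation of treatment.

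The hypotheses in section 2 include "reduced stepping initiation times, greater displacement of the body over the feet during stepping initiation". Section 10b aims for "at least 32 completing the study (16 per group"), while section 10a says "Approximately 30 patients will be enrolled in the study".

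**The concern.** In a two-group, two-session design, a difference in improvement between groups is the Group-by-session interaction. Its F statistic is the square of the t statistic comparing post-minus-pre change between groups. The pre-test is therefore used, but only by subtracting it in full, as if each extra unit at baseline carried one extra unit to the post-test. When the true slope is below 1, subtraction over-corrects and adds baseline noise to the comparison. ANCOVA estimates the slope from the same data.

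This is a question of precision; the planned test is not biased under proper randomization. Precision matters here because the target is 16 completers per group, section 10b gives no power calculation, and an unspecified multiplicity correction will take more power away. Two of the three hypotheses, on stepping initiation time and on displacement of the body over the feet, fall under this analysis.

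**Working it through.** **Inputs from the documents.** 32 completers, 16 per group, and up to 20% withdrawal (section 10b). The plan's own figure reproduces: 32 / (1 − 0.20) = 40 patients approached. Applying the same 20% to the 30 enrolled in section 10a gives 30 × 0.8 / 2 = 12 per group, used below as a second, assumed case.

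**Inputs not in the documents.** The pre/post correlation r and the ratio k of post-test SD to pre-test SD. Ranges are shown for both.

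**Identity.** In a test data set of 16 per group, the interaction F(1,30) was 3.6732 and the squared change-score t was 3.6732.

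**Variances.** Set the pre-test SD to 1 and the post-test SD to k.

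- Change score: 1 + k² − 2rk
- ANCOVA residual: k²(1 − r²)
- Difference: (1 − rk)², never negative

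ANCOVA can therefore lose only by having to estimate the slope. With a normal baseline and a common slope, the expected inflation with n per group is 1 + 1/(2n − 4): 1 + 1/28 = 1.0357 at 16 and 1 + 1/20 = 1.050 at 12. This cap holds for any k and is reached when rk = 1.

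**ANCOVA variance divided by change-score variance, 16 per group**

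| k | r = 0.3 | 0.5 | 0.7 | 0.8 | 0.9 |
|---|---|---|---|---|---|
| 0.9 | 0.60 | 0.69 | 0.78 | 0.82 | 0.84 |
| 1.0 | 0.67 | 0.78 | 0.88 | 0.93 | 0.98 |
| 1.1 | 0.74 | 0.85 | 0.95 | 1.00 | 1.04 |
| 1.25 | 0.81 | 0.93 | 1.02 | 1.04 | 0.98 |

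With k = 1 the ratio is [(1 + r)/2] × 1.0357; at r = 0.5 that is 0.75 × 1.0357 = 0.777. Break-even is r = 2/1.0357 − 1 = 0.931 (0.905 at 12 per group). Change scores are slightly better for r of about 0.79 to 0.96 at k = 1.1, and 0.66 to 0.89 at k = 1.25. Counting the lost degree of freedom (30 to 29), the worst case is 3.9% on squared confidence-interval width and break-even at k = 1 is 0.925.

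**Illustrative power.** Assumed effect 0.8 pre-test SD, k = 1, 16 per group. The second alpha stands in for the unspecified multiplicity correction.

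| r | alpha 0.05: change / ANCOVA | alpha 0.005: change / ANCOVA |
|---|---|---|
| 0.3 | 46% / 62% | 15% / 27% |
| 0.5 | 59% / 70% | 25% / 34% |
| 0.7 | 81% / 85% | 47% / 54% |
| 0.8 | 93% / 95% | 70% / 74% |

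The largest power loss for ANCOVA in the alpha 0.05 grid is 1.3 points (k = 1.25, r = 0.8: 83.1% against 81.8%). Simulation with 60,000 trials per cell agrees within 0.5 points, and both tests reject 4.8% to 5.3% of the time under the null.

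**Timed Up and Go.** It is an outcome (section 3) and an entry criterion: "Subjects with a Timed up and go test > 12 seconds" (section 10c). If the screening value is also the pre-test, which is not stated, selection narrows the pre-test SD and raises k. With normal scores and an unselected r of 0.7:

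- lower quarter excluded: r = 0.583, k = 1.202, ratio 0.95
- lower half excluded: r = 0.509, k = 1.376, ratio 0.97

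At an unselected r of 0.9 the ratios are 1.007 and 1.016. The gain for this outcome may be only 3% to 5%, or a 1% to 2% loss.

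**The case against.** The strongest reply is that nothing is broken. The Group-by-session ANOVA is a legitimate randomized pre/post analysis, and the size of any gain rests on r and k, which the documents do not give. The 0.93 threshold needs equal SDs, and the one outcome where the documents bear on k, Timed Up and Go, points to a near-nil gain. The power figures rest on an assumed effect and an assumed alpha, and the largest gains sit at the lowest r shown. All of this stands, and it limits the claim to precision of unknown size.

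Three further points carry less weight.

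- **Stepping initiation time.** No section names it as an output of the forward-step test. The link is an inference, but a reasonable one: that test uses the Limits of Stability report, and section 3 says the report includes reaction time.
- **Naming the deciding term.** This could be cured by naming the interaction, without ANCOVA. True; it is a side benefit of the fix.
- **Allocation.** Section 3 allows departures from the random sequence to balance severity, so variance ratios averaged over chance imbalance may not describe this design. Where that balancing also equalizes an outcome's own pre-test, it favours ANCOVA. In a simulation with matched baselines (r = 0.5, k = 1), the change-score test rejected a true null only about 2.5% of the time, while ANCOVA held 5%.

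**Conclusion.** The concern holds, as a matter of efficiency. The trade is lopsided: with equal SDs, ANCOVA saves 12% of variance at r = 0.7, 22% at 0.5 and 33% at 0.3, against an expected loss capped at 3.6% at 32 completers or 5.0% at 24. A 22% saving is worth about 1/0.777 − 1 = 29% more patients. The gain is material if r is about 0.7 or less and k is near or below 1, and small, nil or slightly negative otherwise.

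The cap assumes a normal baseline and a common slope, and is an average over randomizations; a single trial with a large chance imbalance could pay more. The figures do not apply to the questionnaires' two-by-four analysis. ANCOVA does not repair the discretionary departures from the allocation sequence. The change is worth making, with medium confidence because r and k are unknown.

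**What to change.** In section 4, for the outcomes now assigned to the two-by-two ANOVA, define the treatment test as an ANCOVA of the post-test score on group with that outcome's own pre-test score as covariate. Report the adjusted prism-minus-sham difference with its 95% confidence interval. This also settles which term decides.

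Leave the questionnaires' one-month and three-month comparisons in place. If the same adjustment is wanted there, apply it at each post-baseline time with the pre-test as covariate.

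The cost is one or two sentences, one degree of freedom, and the capped slope-estimation loss given above. It needs no new data, and SPSS can fit the model. Settle it before the analysis at 60% completion described in section 3 (Randomization and blinding), because a switch made after the other researchers are unblinded could look data-driven.
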